3.1 Rationale

Exenatide is an injectable glucagon-like peptide 1 (GLP-1) receptor agonist approved as an adjunct to diet and exercise to improve glycemic control in adults with type 2 diabetes mellitus (T2DM) by the United States and Europe. Byetta (exenatide twice daily) is administered as a subcutaneous injection within 1 hour before the two main meals of the day, approximately 6 hours or more apart. Treatment is typically initiated at 5 mcg per dose, twice daily, and may be increased to 10 mcg twice daily based on the patient’s clinical response.

During Health Canada’s review of the marketing authorisation application of exenatide, Lilly provided a commitment to monitor the off-label use and compliance to the Summary of Product Characteristics (SPC) of exenatide prescriptions through a post-launch utilization study. Specifically, Health Canada requested that:

The RMP should be revised to include a post-marketing study conducted on exenatide use and adherence to labeling recommendations in Canada, similar to the drug utilization study requested by the EU Regulatory authority that is currently ongoing in various EU countries. Since preliminary information has already indicated off label use of exenatide with either TZD or insulin in the EU, the need for further study and/or additional risk management actions with these products should be specifically addressed.

Table 1: Canadian Byetta Indication

Byetta Monograph
Indication and Clinical Use:
BYETTA is indicated in combination with metformin and/or sulfonylurea to improve glycemic control in patients with type 2 diabetes mellitus, when maximally tolerated doses of these oral therapies in addition to diet and exercise do not provide adequate glycemic control.
BYETTA is indicated in combination with insulin glargine (with or without metformin) to improve glycemic control in patients with type 2 diabetes mellitus when insulin glargine (with or without metformin) in addition to diet and exercise, does not provide adequate glycemic control
Contraindication:
BYETTA should not be used in the pediatric patient population.

BYETTA should not be used in patients with end-stage renal disease or severe renal impairment (creatinine clearance <30 mL/min), including patients receiving dialysis

BYETTA is contraindicated in patients with diabetic ketoacidosis, diabetic coma/precoma or type 1 diabetes mellitus.

Source: Byetta Drug Product Monograph, Canadian Pharmacists Association, online version, April 2011.

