3.3 Data Source

The proposed study will utilize data from the IMS Brogan's Longitudinal Patient Data assets (LRx). LRx tracks the prescription activity of anonymized patients over time (longitudinally), with records dating back to 2004. Collection of prescriptions that include anonymized patient data from approximately 4,000 pharmacies nationwide enables visibility to all payer types and is ideally suited to provide insights into chronic, retail-based markets. LRx data is un-projected and is based on a large sample (~75% coverage nationally, see table 1). By tracking patient prescription history, LRx goes beyond measuring prescription volumes to tracking real-world behaviour and use.

Table 2: Coverage of LifeLink (LRx) Patient Longitudinal Database

Region	% Coverage
	As a % of projected Rx volume in CompuScript – MAT Dec 2011
Total Canada	74.6%
British Columbia	66.4%
Alberta	68.8%

Saskatchewan	71.9%
Manitoba	79.6%
Ontario	75.8%
Quebec	76.7%
New Brunswick	95.7%
Nova Scotia	67.2%
Newfoundland / PEI	53.1%

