3.4.4 Study Outcomes and Definitions

[figure not shown]
The primary outcome of interest is the off label use of Byetta in Canada.

A patient's therapy type will be inferred by identifying if a patient switches between, or adds on to therapies, as shown in figure 3.

Mono Therapy is defined as a patient receiving a specific therapy (Therapy 1) prior to a different therapy (Therapy 2) where Therapy 1 is not detected after Therapy 2 initiation. Mono therapy for this study, refers to a patient received a prescription for only one product at a given time.

Concomitant Therapy is defined as a patient receiving a specific therapy (Therapy 1) prior to a different therapy (Therapy 2) where Therapy 1 is detected after Therapy 2 initiation.

Figure 3: Distinguishing between add-on and switch therapies

Patients will be selected for the study if they receive a Byetta script anytime during the analysis period and if they met the inclusion criteria. To identify on-label vs. off-label use, patient history will then be used to classify patients as "inferred on-label" if they also received Metformin and/or SU or Lantus during the study (Business rules 1 and 2 in Table 5).

All other patients that do not meet the criteria for use of Byetta with metformin and/or SU or Lantus will be classified as “inferred off-label”. The group of patients classified as “inferred off-label” will then be further classified to gain a better understanding of the trends in “inferred off-label” use of Byetta (Business rules 3-10 in Table 5).

The Business rules described in Table 5 are prioritized to ensure the appropriate classification of each patient. Therefore patients will be classified based on the highest rank business rule. For example, if a patient receives scripts for both Metformin and other insulin during the analysis period, they will be classified as “inferred on-label” as they have a script for metformin and therefore are classified by business rules 1 and 2

Note: The patient classification categories (‘Inferred Adherence Label’) can be modified in the initial phase of the project.

Table 5: Business rules applied to classify patients as “on-label” vs. “off-label”

(The business rules have been structured to align with the Canada monograph for Byetta indication and clinical use (see Table 1) and will be finalized upon study initiation).

Rank	Business Rules	Cohort Description	Inferred Adherence Label

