1	Concomitant use of* Byetta with metformin (met) and/or sulfonylurea (SU), OR Concomitant use of Byetta with Lantus	Met and/or SU or Lantus is prescribed with Byetta	Inferred On-label
2	Evidence of** Byetta and metformin and/or sulfonylurea OR Evidence of Byetta and Lantus	Met and/or SU or Lantus is not prescribed with Byetta, but both appear in the analysis period	Inferred On-label
3	Evidence of Byetta and Levemir	Levemir is prescribed in the analysis period	Off-Label Insulin Use
4	Evidence of Byetta and Human Basal Insulin	Human basal insulin is prescribed in the analysis period	
5	Evidence of Byetta and thiazolidinedione (TZD)	TZD is prescribed in the analysis period	Off-Label OAD Use

6	Byetta Alone	No other products prescribed in the analysis period	Inferred Off-label
7	Evidence of Byetta and all other insulin	Other insulin is prescribed in the analysis period	
8	Evidence of Byetta and all other OADs	Other OADs are prescribed in the analysis period	
9	Pediatric Patients	Patient is under the age of 18 (<18)	
10	All other combinations	All other combinations	

Note: Evidence of Diabetic ketoacidosis, diabetic coma/precoma and end stage renal disease cannot be inferred from the dataset; therefore we will not be able to identify these patients as a separate group

* "Concomitant use of..." refers to continued use of Byetta and other product

** "Evidence of..." refers to anytime within the study period including look-back or look forward periods

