3.4.7 Limitations

Based on restrictions in Canada, diagnosis can only be inferred. Therefore on-label and off-label use is an estimation based on the applied rules. The off-label use is likely over-estimated as the rules to include a patient in on-label and stringent and all other patients are considered off-label.

Counter indications such as diabetic ketoacidosis, diabetic coma/precoma and end-stage renal failure cannot be inferred from the data source. Therefore, these patients will not be identified in the study.

There is differing amount of information for each patient due to the fixed time frame of the analysis. Since each patient will have a different index date the amount of data will differ for those patients who initiate Byetta at the start of the analysis period compared to patients who initiate Byetta at the end of the analysis

period. This is ensures we have as much data available as possible for each patient so they can be classified appropriately

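### 'Inferred On-label' tests only for a labelled partner drug; the label's dose and control conditions go untested and undisclosed, and 3.4.7 states only the opposite bias

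*Protocol*

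**What the plan says.** Table 1 in protocol section 3.1 gives two Byetta indications. Use with metformin and/or SU is indicated "when maximally tolerated doses of these oral therapies in addition to diet and exercise do not provide adequate glycemic control". Use with insulin glargine is indicated "when insulin glargine (with or without metformin) in addition to diet and exercise, does not provide adequate glycemic control".

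Section 3.4.4 classifies a patient as 'Inferred On-label' "if they also received Metformin and/or SU or Lantus during the study". Table 5 does this through two ranked rules that share one label. The cohort description for rule 1 is "Met and/or SU or Lantus is prescribed with Byetta", and for rule 2 it is "Met and/or SU or Lantus is not prescribed with Byetta, but both appear in the analysis period". A footnote to Table 5 widens the word 'evidence', which rule 2 uses, to any time in the study period, look-back and follow-up included. The same section states the alignment: "The business rules have been structured to align with the Canada monograph for Byetta indication and clinical use".

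Section 3.4.7 says that diagnosis is inferred, that on- and off-label status is therefore an estimate, and that the amount of data differs by index date. It adds: "Counter indications such as diabetic ketoacidosis, diabetic coma/precoma and end-stage renal failure cannot be inferred from the data source". On bias it makes one directional statement: off-label use is probably over-estimated, because the on-label rules are strict and everyone else falls into off-label.

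**The concern.** The primary objective (3.2.1) is use outside the labelled indications, and 3.1 shows that the study answers a Health Canada request about adherence to labelling. The classifier checks one element of each indication, the partner drug. A patient who has the partner drug but does not meet the remaining conditions is counted as adherent.

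Two consequences follow. The 'Inferred On-Label' percentage in Table 6 is likely to be read as adherence to the indication when it measures the presence of a permitted partner drug. And the only bias statement tells the regulator that the off-label figure errs on the high side, although the on-label rules contain a source of error that pushes it down.

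**Working it through.** The plan gives no expected off-label rate, so there is no figure to reproduce. The check is a comparison of passages, followed by simple algebra on the direction of bias.

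**Step 1: label conditions (Table 1, 3.1) against the rules (Table 5, 3.4.4) and the limitations (3.4.7).**

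| Condition | Metformin/SU indication | Glargine indication | Tested by rules 1–2 | Named in 3.4.7 |
|---|---|---|---|---|
| Partner drug present | required | required | yes | not applicable |
| Maximally tolerated oral dose | required | not required | no | no |
| Inadequate control on the partner therapy | required | required | no | no |

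Section 3.3 describes prescription records and mentions no glycaemic measure, so the control condition cannot be derived from the source as described. Whether strength and quantity are held is not stated.

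**Step 2: timing.** Rule 1 needs continued use of both products. The definition of concomitant therapy in 3.4.4 needs one therapy before the other starts and still detected afterwards, but it does not fix which of the two is Byetta. Rule 2 drops concurrency altogether. Its cohort description refers to the analysis period, while the footnote allows the whole study period. On either reading, a patient whose first metformin, SU or Lantus fill comes after Byetta start is 'Inferred On-label'. For such a patient the records show no partner therapy on which control could have been inadequate when Byetta was started.

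**Step 3: direction of bias.** Let
- U = share reported as off-label (all off-label categories together);
- f = share of 'Inferred On-label' patients who fail a dose or control condition that applies to them;
- g = share of reported off-label patients who are in truth on-label, for example because their metformin was filled at a pharmacy outside the database.

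True off-label share = U(1 − g) + f(1 − U).

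The reported figure is too high, as 3.4.7 says, only if gU > f(1 − U), that is, if g > f(1 − U)/U.

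None of U, f or g is in the documents. The values of U and f below are assumed, only to show how the condition behaves.

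| U | f | True share if g = 0 | g needed for 3.4.7 to hold |
|---|---|---|---|
| 10% | 10% | 0.10 + 0.10 × 0.90 = 19% | above 0.09/0.10 = 90% |
| 10% | 20% | 0.10 + 0.20 × 0.90 = 28% | above 0.18/0.10 = 180%, impossible |
| 20% | 10% | 0.20 + 0.10 × 0.80 = 28% | above 0.08/0.20 = 40% |
| 20% | 30% | 0.20 + 0.30 × 0.80 = 44% | above 0.24/0.20 = 120%, impossible |
| 40% | 10% | 0.40 + 0.10 × 0.60 = 46% | above 0.06/0.40 = 15% |
| 40% | 30% | 0.40 + 0.30 × 0.60 = 58% | above 0.18/0.40 = 45% |

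So the statement in 3.4.7 can be true or false, depending on quantities that the plan neither gives nor measures. The error represented by g is real: national coverage in Table 2 (3.3) is 74.6% of prescription volume, and Table 3 (3.4.3) acknowledges that patients fill at more than one pharmacy.

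**The case against.** The strongest reply is that the protocol is open about its method. The reported term is 'Inferred On-Label', the criterion is written out in 3.4.4, and 3.4.7 calls the classification an estimate. Glycaemic control cannot be read from prescription records, so the gap cannot be designed away. The rules are also to be finalised at study initiation, and extra tables may sit in an analysis plan that is not at hand.

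Much of this stands, and it limits the remedy to wording plus one split by date. It does not remove the point. The general caveat is tied to inferred diagnosis and does not say that label conditions were left untested. The protocol names unobservable contraindications specifically, in both 3.4.4 and 3.4.7, so specific disclosure is its own standard. The rules, the alignment claim and the bias statement are all fixed in this document.

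A reader might infer several stronger points, which the documents do not support:
- That the on-label percentage is an upper bound on adherence. Partner fills at uncaptured pharmacies put truly on-label patients into off-label, so no bound follows.
- That off-label use is under-reported on balance. Step 3 shows that this depends on unknown quantities.
- That 3.4.7 covers contraindications alone. It also covers inferred diagnosis and unequal observation time.
- That the maximal-dose condition applies to every patient. It belongs to the metformin/SU indication only, and a patient also on Lantus may qualify under the glargine indication.
- That a single metformin fill on the day Byetta starts is handled exactly like established therapy. It would probably reach rule 2 rather than rule 1, although both carry the same label.

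**Conclusion.** The point holds as one of classification and disclosure. 'Inferred On-label' means that a labelled partner drug appears in the records, in some cases only after Byetta started. It does not establish that the indication was met. The untested conditions are inadequate control (both indications) and maximally tolerated oral dose (metformin/SU only). They are not named in 3.4.7, and this source of error runs against the direction stated there.

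No size can be given. The percentages in the working rest wholly on assumed U and f and show only that the direction is open. The conclusion itself rests on the text of Table 1, Table 5 and 3.4.7 and needs no assumption about prescribing behaviour, except that the downward pull is zero if no 'Inferred On-label' patient fails a condition.

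**What to change.** 1. In Table 6, and in the matching column of Table 7, describe the 'Inferred On-Label' group as 'labelled partner drug present'. In 3.4.4, qualify the alignment claim: the rules reflect the partner-drug element of the indication and do not test dose or control.
2. In 3.4.7, name the two unverified conditions and the indication to which each applies. Replace the over-estimation sentence with a statement that error runs in both directions and that the net direction is unknown. Do not call the figure an upper bound.
3. Using fill dates, split the group into patients whose first recorded metformin, SU or Lantus fill precedes Byetta start and those whose first such fill is on or after it, and report both counts. The split is descriptive: an earlier fill does not prove that the indication was met, and a later one may reflect earlier fills at another pharmacy.
4. Optionally, describe the dispensed dose of the partner drug, only if LRx holds strength and quantity. This needs no threshold and should not be used to reclassify anyone.

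The cost is revised wording, one extra split of a table and a narrower headline claim. The split needs only dates that the look-back requirement and the add-on/switch logic already use.

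### Table 5 ranks 1 and 2 count Byetta with Lantus and a sulfonylurea as on-label, a combination that Table 1 does not name, because they set no condition on further agents

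*Protocol*

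**What the plan says.** Table 1 (protocol section 3.1) sets out two indications. The first reads "BYETTA is indicated in combination with metformin and/or sulfonylurea to improve glycemic control in patients with type 2 diabetes mellitus". The second reads "BYETTA is indicated in combination with insulin glargine (with or without metformin) to improve glycemic control in patients with type 2 diabetes mellitus". The first names no insulin; the second names metformin as the only oral partner.

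Section 3.4.4 says of Table 5 that "The business rules have been structured to align with the Canada monograph for Byetta indication and clinical use". Rank 1 assigns inferred on-label to "Concomitant use of* Byetta with metformin (met) and/or sulfonylurea (SU), OR Concomitant use of Byetta with Lantus". Rank 2 gives the same label when the drugs are not used together but are both found; the table's footnote lets that evidence come from anywhere in the study period, look-back and follow-up included.

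Overlaps are settled by rank: "patients will be classified based on the highest rank business rule". Section 3.4.7 says of the resulting bias: "The off-label use is likely over-estimated as the rules to include a patient in on-label and stringent".

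**The concern.** The primary outcome is off-label use, and Table 5 is the instrument that measures it. A patient on Byetta, Lantus and an SU meets both arms of rank 1, yet neither indication in Table 1 describes that regimen. No off-label rank describes it either, so moving the off-label ranks above ranks 1 and 2 would not catch it.

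The regimen contains insulin. The regulator's request in section 3.1 singles out off-label use with TZD or insulin, and section 3.2.2 makes co-use with either the secondary objective. If the regimen lies outside the label, the study counts an insulin combination of direct interest as adherent. The error would then run against the direction of bias that section 3.4.7 tells the reader to expect.

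**Working it through.** The protocol states no expected percentage, so there is no figure to reproduce. The check compares the rule with the label wording, combination by combination.

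**Inputs.**
- Rule (Table 5, ranks 1 and 2): on-label if metformin, SU or Lantus is present, whatever else is taken.
- Label (Table 1, read literally): metformin; SU; metformin with SU; Lantus; Lantus with metformin.

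**Enumeration.** Three drugs, each present or absent, give 2^3 = 8 combinations.

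| Taken with Byetta | Ranks 1–2 | Named in Table 1 |
|---|---|---|
| none of the three | not on-label | no |
| metformin | on-label | yes |
| SU | on-label | yes |
| metformin + SU | on-label | yes |
| Lantus | on-label | yes |
| Lantus + metformin | on-label | yes |
| Lantus + SU | on-label | **no** |
| Lantus + SU + metformin | on-label | **no** |

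The rules accept 7 and Table 1 names 5. The 7 − 5 = 2 that differ both contain Lantus with SU. No combination differs in the other direction.

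**Wider setting.** Adding other insulin, TZD and other OADs gives 2^6 = 64 combinations. The rules call 64 − 2^3 = 56 on-label, and Table 1 still names 5, so 56 − 5 = 51 differ. Of these, 2^4 = 16 contain Lantus with SU. The other 51 − 16 = 35 come from the same absence of any condition on further agents. They include metformin or SU with another insulin or a TZD, which is the separate question of rank order. These are counts of combinations, not of patients.

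**Effect on the result.** Let p be the reported off-label percentage and q the percentage of Byetta patients with concomitant Lantus and SU, with or without metformin. Moving them gives p + q. The documents give neither value. With p = 10 assumed:

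| q (assumed) | 1 | 2 | 5 | 10 |
|---|---|---|---|---|
| p + q | 11 | 12 | 15 | 20 |

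**Can q be recovered from the tables shown?** Table 6 does not separate the regimen. Table 7 has an SU row and an insulin row under the inferred on-label column, but no joint row and no Lantus row. The smaller of those two counts is an upper limit for the regimen; the count itself is not available.

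**The case against.** **Table 1 does not exclude glargine with SU.** It does not name the combination, and its contraindications concern other matters. A reader might infer that the regimen is off-label as a matter of fact. The documents do not establish that: it depends on reading each indication as the whole permitted combination. The parenthesis about metformin favours that reading, and the protocol treats other insulins taken without metformin, SU or Lantus as off-label (ranks 3, 4 and 7). It remains a reading, so the claim of under-counting is conditional. The mismatch between the two tables is not.

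**Accepting further agents is a declared principle.** Section 3.4.4 gives the example of metformin with other insulin and counts it on-label. This shows that the word OR is not the cause, as a reader might suppose. Two separate ranks would give the same label, because SU alone or Lantus alone is enough. The cause is the lack of a condition on further agents, combined with the ranking. The example does not mention Lantus with SU, and declaring the principle does not make it agree with Table 1.

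**The regimen is partly visible.** It would be too strong to say that the tables hide it, since Table 7 reports SU and insulin use separately among on-label patients. Only the joint count is lost.

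**Rank 2 evidence may be sequential.** This stands. An SU stopped during look-back and Lantus started later are not a combination, so rank 2 patients should not be counted with the concomitant regimen.

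**The rules are to be finalised at study initiation.** This makes correction easy, but the text as it stands still claims alignment.

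**Conclusion.** The point holds in a limited form. Ranks 1 and 2 label Byetta with Lantus and SU, with or without metformin, as inferred on-label, and Table 1 does not name that regimen. For these two combinations Table 5 does not align with Table 1 as section 3.4.4 says it does.

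If the indications are read as exhaustive, the off-label percentage is too low by q points, opposite to the over-estimation stated in section 3.4.7. If they are not, this regimen causes no bias, but the protocol should say so. The size is unknown: 11% to 20% in place of 10% rests wholly on the assumed q of 1 to 10 and is not an estimate. The point concerns how the study classifies patients. It does not say which regimen is appropriate.

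**What to change.** - Reconcile Table 5 ranks 1 and 2 with Table 1 for this regimen, and state which reading of the indications the study adopts.
- Add a category to Tables 5, 6 and 7 for concomitant Byetta, Lantus and SU, with or without metformin. In Table 5 it must be tested before the present rank 1, or rank 1 will absorb it.
- In Table 6, report the on-label and off-label percentages twice, with this category counted each way.
- Define the category on concomitant use of both drugs with Byetta. Show rank 2 patients with any-time evidence of both drugs separately.
- Qualify the statement on direction of bias in section 3.4.7 accordingly.

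The handling of metformin or SU with other insulins or with TZD should be left to the question of rank order. Barring all insulin from the metformin/SU arm would overturn the worked example in section 3.4.4, and this point does not support so large a change.

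The cost is one extra row and a reworded rank; Lantus and SU are already tracked in Table 4. The off-label percentage may have to be shown as a range, and it may rise.

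### Table 5 Rank 2 labels patients on-label when the partner drug was not prescribed with Byetta, and its time window is stated two ways

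*Protocol*

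**What the plan says.** Table 1 in the Protocol, section 3.1, gives two approved uses: "BYETTA is indicated in combination with metformin and/or sulfonylurea to improve glycemic control in patients with type 2 diabetes mellitus", and "BYETTA is indicated in combination with insulin glargine (with or without metformin) to improve glycemic control in patients with type 2 diabetes mellitus". Section 3.4.4 says that the Table 5 rules were built to match this monograph text.

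Section 3.4.4 separates a switch from an add-on. In mono therapy the first drug is no longer seen once the second has started. Concomitant therapy is the case "where Therapy 1 is detected after Therapy 2 initiation".

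Table 5 then ranks the rules, and each patient takes the label of the highest rank met:

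- Rank 1 is concomitant use with metformin, SU or Lantus. It is labelled Inferred On-label.
- Rank 2 is evidence of Byetta and one of those drugs, with the description "Met and/or SU or Lantus is not prescribed with Byetta, but both appear in the analysis period". It is also labelled Inferred On-label.
- Rank 6 is Byetta alone, described as "No other products prescribed in the analysis period". It is off-label.

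The double-asterisk footnote says that evidence "refers to anytime within the study period including look-back or look forward periods". Tables 6 and 7 (section 3.4.6) have one on-label category, with no split between Ranks 1 and 2. Section 3.4.7 says that off-label use is probably over-estimated, because the on-label rules are strict.

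**The concern.** Off-label use is the primary outcome, and the study answers a commitment to the regulator about adherence to the label. The label asks for combination use. Rank 2 gives on-label status to patients whom its own description places outside combination use, and it takes them before Rank 6 can. Because the two ranks share a label and a table row, a reader of the report could not undo this.

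The second problem is reproducibility. The description column and the footnote give Rank 2 different windows, so two programmers who each follow the text could give the same patient opposite labels on the primary outcome.

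**Working it through.** The plan states no figure that bears on this point, so there is nothing to reproduce. The check applies the rules as written.

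**Two patients.** Month 1 is June 2011 (section 3.4.2), so Year 1 runs from June 2011 to May 2012. Assume that each patient passes Table 3 and fills no other diabetes drug.

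- Patient A last fills metformin in June 2011 and takes only Byetta from July 2011. Section 3.4.4 calls this mono therapy after a switch. Both fills lie in the analysis period, so Rank 2 applies under either window and the patient is on-label.
- Patient B last fills metformin in May 2011 and takes only Byetta from July 2011. By the description columns Rank 2 fails and Rank 6 applies: off-label. By the footnote Rank 2 applies: on-label.

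**Window lengths.** The analysis period is 12 months. Adding the minimum look-back and follow-up at its two ends gives 6 + 12 + 3 = 21 months.

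**All patterns.** Partner-drug fills (metformin, SU or Lantus) can occur in four places: before the analysis period, in it but not with Byetta, with Byetta, or only in follow-up after Byetta has stopped. That makes 2^4 = 16 patterns. In 8 there is a fill with Byetta, so Rank 1 applies under either window. The other 8, for patients with no other diabetes drug and with concomitant read as the single-asterisk footnote defines it, are:

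| Before period | In period, not with Byetta | Follow-up only | Analysis-period window | Study-period window |
|---|---|---|---|---|
| no | no | no | Rank 6, off | Rank 6, off |
| no | no | yes | Rank 6, off | Rank 2, on |
| no | yes | no | Rank 2, on | Rank 2, on |
| no | yes | yes | Rank 2, on | Rank 2, on |
| yes | no | no | Rank 6, off | Rank 2, on |
| yes | no | yes | Rank 6, off | Rank 2, on |
| yes | yes | no | Rank 2, on | Rank 2, on |
| yes | yes | yes | Rank 2, on | Rank 2, on |

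On-label: 4 of 8 under the narrow window and 7 of 8 under the wide one. The 3 that change are look-back only, follow-up only, and both. These count patterns, not patients.

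**Add-on versus switch.** Concomitance enters Table 5 only at Rank 1. Under the footnote window, everyone who meets Rank 1 also meets the evidence condition of Rank 2, so deleting Rank 1 would change nobody's on-label or off-label status.

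**Size.** Let r1 and r2 be the shares of patients at Ranks 1 and 2, and t the unknown fraction of Rank 2 patients who are true combination users.

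- Off-label as planned: 1 − r1 − r2.
- Off-label with Rank 2 counted as off-label: 1 − r1.
- Understatement due to Rank 2: r2 × (1 − t).

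The protocol gives none of these. As an assumed illustration, let 30% of patients have no detected concomitant partner drug, and let Rank 2 take a fraction f of them. Reported off-label use is 30% × (1 − f):

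| f | 0 | 0.25 | 0.50 | 0.75 | 1 |
|---|---|---|---|---|---|
| Reported off-label | 30% | 22.5% | 15% | 7.5% | 0% |

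At f = 0.50, r2 is 15%. The understatement is 15 points if t = 0 and 7.5 points if t = 0.5.

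**The case against.** The strongest defence is that Rank 2 rescues real combination users. LRx covers 74.6% of prescription volume nationally (Table 2), and Table 3 recognises that patients fill at other pharmacies, so a true partner-drug fill can go unseen. The protocol does not give this as its reason, but the point stands: Rank 2 patients are not all misclassified. A reader might infer that each percentage point at Rank 2 is a point lost from off-label use. That needs t = 0, which the documents do not support.

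A second defence is that the footnote governs. It defines the rule's own term, the section text speaks of drugs received during the study, and Rank 2 precedes Rank 6. This makes the wide window the likelier intent. But the description columns of Ranks 2 and 6 both name the analysis period, as does the worked example in section 3.4.4, so the text remains contradictory. That the rules are to be finalised at study initiation leaves time to correct them; it does not reconcile them.

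Three further inferences are tempting but not supported:

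- That very distant fills confer on-label status, such as metformin 17 months before a May 2012 Byetta start or 14 months after a single June 2011 fill. The 12 Month Gap criterion in Table 3 removes such patients unless they filled other diabetes drugs in between. Patients A and B have short gaps and do not depend on this.
- That Rank 1 is equally loose because section 3.4.4 asks only for detection after the second drug starts. The single-asterisk footnote requires continued use of both products, so a return to metformin after Byetta has stopped does not qualify. At most the two wordings should be aligned.
- That the 3-month follow-up does nothing. Under the footnote window, follow-up fills can decide Rank 2, and section 3.4.2 ties follow-up to concomitant insulin or TZD use.

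**Conclusion.** The point holds in two parts. First, Rank 2 assigns on-label status without combination use, against Table 1 and against the plan's own treatment of Byetta alone. The switch versus add-on distinction therefore does not affect the primary result. Second, the Rank 2 window is contradictory, and patients whose only partner-drug fill falls outside the analysis period can be labelled either way.

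The error introduced by Rank 2 runs toward fewer off-label patients, so the blanket statement in section 3.4.7 is not supported. Its size cannot be derived from the document: it is r2 × (1 − t), with both terms unknown, and the percentages above rest on an assumed 30%. Nor do the documents justify moving every Rank 2 patient to off-label, since that sets t to zero. Reporting both bounds is what the evidence allows.

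**What to change.** 1. State one window, in the same words, in the Table 5 rules, cohort descriptions and footnotes, including the other ranks that rest on evidence of use.
2. Report Rank 2 as its own category in Tables 6 and 7, for example as sequential or not shown to be combined, and do not merge it into Inferred On-label.
3. Give off-label use twice, with Rank 2 counted as off-label (strict) and as on-label (permissive).
4. Rewrite the sentence on direction of bias in section 3.4.7 to say that Rank 2 can lower the off-label estimate, while uncaptured fills can raise it.

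The cost is an extra row in Table 6 and column in Table 7, and a range in place of a single percentage. No new data are needed. A rule based on overlapping supply would be sharper, but it relies on days' supply, which the protocol does not mention, so the fix does not depend on it.
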